## Physical Description of Study Intervention(s)

### *Guselkumab*

The guselkumab supplied for this study is a sterile liquid for SC injection in a single-use PFS. Each single-use PFS is 1 mL glass syringe with a 27 gauge, 1/2 inch fixed needle and a latex-free rigid needle shield and contains CCI of guselkumab with either a 1 mL fill of liquid for the PFS-U (CCI). No preservatives are present. Guselkumab will be manufactured and provided under the responsibility of the sponsor. Refer to the guselkumab IB for a list of excipients in the drug product.

Placebo is supplied as a sterile liquid for SC injection at a fill volume of 1.0 mL in single-use PFS-U or CCI. Each placebo PFS contains the same excipients as the drug product.

### *ENBREL (etanercept)*

Commercial etanercept (ENBREL) will be supplied as an active comparator to the study sites. Details on etanercept are available in the etanercept (ENBREL) package insert in the Site Investigational Product Procedures Manual.

## Packaging

Two dosage forms for guselkumab and placebo will be used in this study, PFS-U and CCI assembled with a PFS. Both dosage forms will be packaged in individual participant kits in tamper evident packaging.

Etanercept (ENBREL) will be provided in commercial primary packaging. Secondary packaging may be changed to facilitate clinical labeling.

Study intervention administration must be captured in the source documents and the case report form (CRF). Study-site personnel will instruct participants on how to store study intervention for at-home use as indicated for this protocol.

For details on rescue medications, refer to Section 6.5.1, Rescue Medication. For a definition of study intervention overdose, refer to Section 8.4, Treatment of Overdose.

### 6.2. Preparation/Handling/Storage/Accountability

Study intervention labels will contain information to meet the applicable regulatory requirements.

All study intervention must be stored at controlled temperatures ranging from 36°F to 46°F (2°C to 8°C), not frozen, and protected from light. Vigorous shaking of the product should be avoided. The sterile product does not contain preservatives and is designed for single use only. Prior to administration, the product should be inspected visually for particulate matter and discoloration. If discoloration (other than a slight yellow color), visible opaque particles, or other foreign particles are observed in the solution, the product should not be used. Study intervention in PFS-U and CCI will be ready to use. Aseptic procedures must be used during the preparation and administration of the study material. Exposure to direct sunlight should be avoided during preparation and administration.

Further details regarding the preparation and storage of guselkumab and placebo will be provided in the Site Investigational Product Procedures Manual. Further details regarding the preparation and storage of etanercept can be found in the ENBREL package insert in the Site Investigational Product Procedures Manual.

The investigator is responsible for ensuring that all study intervention received at the site is inventoried and accounted for throughout the study. The dispensing of study intervention to the participant, and the return of study intervention from the participant (if applicable), must be documented on the drug accountability form. Participants, or their legally acceptable representatives where applicable, must be instructed to return all original containers, whether empty or containing study intervention. The study intervention administered to the participant must be documented on the drug accountability form. All study intervention will be stored and disposed of according to the sponsor's instructions. Study-site personnel must not combine contents of the study intervention containers.

Study intervention must be handled in strict accordance with the protocol and the container label and must be stored at the study site in a limited-access area or in a locked cabinet under appropriate

environmental conditions. Unused study intervention must be available for verification by the sponsor's study site monitor during on-site monitoring visits. The return to the sponsor of unused study intervention will be documented on the drug return form. When the study site is an authorized destruction unit and study intervention supplies are destroyed on-site, this must also be documented on the drug return form.

Potentially hazardous materials such as used ampules, needles, syringes and vials containing hazardous liquids, should be disposed of immediately in a safe manner and therefore will not be retained for drug accountability purposes.

Study intervention should be dispensed under the supervision of the investigator or a qualified member of the study-site personnel, or by a hospital/clinic pharmacist. Study intervention will be supplied only to participants participating in the study. Study intervention may not be relabeled or reassigned for use by other participants. The investigator agrees to neither dispense the study intervention from, nor store it at, any site other than the study sites agreed upon with the sponsor.

### **6.3. Measures to Minimize Bias: Randomization and Blinding**

#### **Intervention Allocation**

##### ***Procedures for Randomization and Stratification***

Central randomization will be implemented in this study. Participants in Part 1a ( $\geq 12$  to  $< 18$  years of age) will be randomized in a 2:1:1 ratio to guselkumab, placebo, or etanercept and participants in Part 1b ( $\geq 6$  to  $< 12$  years of age) will be randomized separately in a 1:1:1 ratio to 1 of same 3 treatment groups using computer-generated randomization schedules, prepared before the study by, or under the supervision of the sponsor. The randomization will be balanced by using randomly permuted blocks and will be stratified by region. The interactive web response system (IWRS) will assign a unique treatment code, which will dictate the treatment assignment and matching study intervention kit(s) for the participant. The requestor must use his or her own user identification and personal identification number when contacting the IWRS and will then give the relevant participant details to uniquely identify the participant.

Randomization will not be used in Part 2 of this study. All participants in Part 2 will receive open-label guselkumab.

#### **Blinding**

For Part 1 of the main study, the investigator will not be provided with randomization codes. The codes will be maintained within the IWRS, which has the functionality to allow the investigator to break the blind for an individual participant.

Data that may potentially unblind the treatment assignment (eg, treatment allocation) will be handled with special care to ensure that the integrity of the blind is maintained and the potential for bias is minimized. This can include making special provisions, such as segregating the data in question from view by the investigators, clinical team, or others as appropriate until the time of database lock and unblinding.

Under normal circumstances, the blind should not be broken until the Week 52 database lock is completed. Otherwise, the blind should be broken only if specific emergency treatment/course of action would be dictated by knowing the treatment status of the participant. In such cases, the investigator may in an emergency determine the identity of the treatment using the IWRS. It is recommended that the investigator contact the sponsor or its designee, if possible, to discuss the particular situation, before breaking the blind. Telephone contact with the sponsor or its designee will be available 24 hours per day, 7 days per week. In the event the blind is broken, the sponsor must be informed as soon as possible. The date and reason for the unblinding must be documented by the IWRS, in the appropriate section of the CRF, and in the source document. The documentation received from the IWRS indicating the code break must be retained with the participant's source documents in a secure manner.

Participants who have had their treatment assignment unblinded should continue to return for scheduled evaluations. The decision to continue or discontinue study treatment for these participants will be based upon consultation of the investigator with the medical monitor.

One interim PK analysis is planned for this study after all participants  $\geq 12$  to  $< 18$  years of age in Part 1a have completed Week 16. This evaluation will be conducted by sponsor personnel who are otherwise not participating in the conduct of this study. Efficacy data will not be analyzed in this interim analysis.

The Sponsor will be unblinded after the last participant in Part 1 has completed their Week 16 visit and the Week 16 DBL has occurred. The investigators, participants, and sponsor site monitors can be unblinded after the last participants in Part 1 and Part 2 have completed the Week 52 visit, and the Week 52 DBL has occurred.

Blinding procedures are not applicable for participants in Part 1 who are randomized to open-label etanercept, with the exception of the blinded efficacy evaluator (see Section 8.1.6), and all participants in Part 2 of the main study who will receive open-label guselkumab and will not be blinded in this study.

#### **6.4. Study Intervention Compliance**

Because guselkumab and placebo will be administered at the investigational site by trained study staff or self-administered by the participant or their caregiver, treatment compliance for these study interventions will be controlled by site personnel.

From Week 0 through Week 52, it is expected that all visits will occur within a range of  $\pm 7$  days of the scheduled visit. Any visits outside of these ranges should be discussed with the sponsor. If a study visit occurs outside the specified visit window, the participant should then resume his or her normal dose schedule relative to the baseline visit (Week 0) as soon as possible. All other follow-up study visits should occur within  $\pm 14$  days of the scheduled study visit. Any out-of-range visit should be documented in the participant's source notes. Guidelines for study intervention administration affected by the COVID-19 pandemic are found in [Appendix 22](#) (Section 10.22).

Study-site personnel will maintain a log of all study intervention administered. Drug supplies for each participant will be inventoried and accounted for. Information regarding study intervention administrations that are administered outside of the scheduled windows or missed will be recorded. Participant charts and worksheets may be reviewed and compared with the data entries on the CRFs to ensure accuracy. Although it is understood that treatment may be interrupted for many reasons, compliance with the treatment schedule is strongly encouraged.

When etanercept is administered by the participant or caregiver away from the site, the amount of study intervention dispensed will be recorded and compared with the amount returned and the participant or caregiver will be asked to record administration information on a paper questionnaire. Etanercept dosing should occur within a range of  $\pm 3$  days of the scheduled date. Participants (and parent/caregiver) will receive instructions on compliance with study treatment when they begin self-administration of etanercept at home. During the course of the study, the investigator or designated study research personnel will be responsible for providing additional instruction to reeducate any participant who is not compliant with taking the study intervention.

## **6.5. Concomitant Therapy**

Concomitant therapies must be recorded throughout the study from screening and continuing until 12 weeks after the last dose of study intervention. Concomitant therapies should also be recorded beyond that point only in conjunction with SAEs that meet the criteria outlined in Serious Adverse Events in Section 8.3.1, Time Period and Frequency for Collecting Adverse Event and Serious Adverse Event Information.

All therapies (prescription or over-the-counter medications, including vaccines, vitamins, herbal supplements) different from the study intervention, as well as all shampoos used to treat plaque psoriasis, moisturizers, or emollients, must be recorded in the CRF. Modification of an effective preexisting therapy should not be made for the explicit purpose of entering a participant into the study.

If a prohibited therapy is administered during the active treatment phase including the LTE, unless agreed to by the medical monitor, the participant should be discontinued from study treatment. If a prohibited therapy is initiated during the safety follow-up period (12 weeks between last administration of study intervention and final site visit), the participant should still complete his or her final study visit, and the medication should be recorded as a concomitant medication.

### **6.5.1. Rescue Medication**

In Part 1 of the study, participants with a PASI score increase of  $\geq 50\%$  from their baseline PASI score at Week 8 or Week 12 will be allowed to use a topical steroid as rescue treatment, with the exception of ultra-high potency topical steroids (eg, clobetasol propionate, halobetasol propionate) which are not allowed at any time. It is recommended that participants use no more than 60 grams of topical steroid per week. In addition, participants should be managed using the lowest possible potency and frequency of rescue topical steroid. Participants must discontinue the use of rescue topical steroids by Week 20 (should not initiate rescue topical steroids at or after Week 16).

### **6.5.2. Topical Therapies for Psoriasis**

With the exception of the use of topical steroids by participants who qualify for rescue therapy (see Section 6.5.1, Rescue Medication), topical therapies that could affect psoriasis or the IGA evaluation (eg, corticosteroids, tar, anthralin, calcipotriene, tazarotene, methoxsalen, pimecrolimus, tacrolimus, and traditional Taiwanese, Korean, or Chinese medicines) are not permitted at any time during the study. The only allowable concomitant treatments on areas affected by plaque psoriasis throughout the study are shampoos (containing tar or salicylic acid only) and topical moisturizers. Participants should not use these topical agents (shampoos, moisturizers) on the day of a study visit. Nonmedicated shampoos may be used on the day of the study visit.

### **6.5.3. Phototherapy or Systemic Therapies for Psoriasis**

The use of phototherapy or systemic antipsoriatic medications is not permitted at any time during the study. These medications include those targeted for reducing TNF $\alpha$  (including but not limited to infliximab or adalimumab), drugs targeted for reducing IL-12, IL-17A, IL-17R, or IL-23 (including but not limited to ustekinumab, tildrakizumab [MK3222], risankizumab [BI-655066], ixekizumab [LY2439821], or brodalumab [AMG827]), alpha-4 integrin antagonists (including but not limited to natalizumab), apremilast, steroids, any conventional systemic therapy that could affect psoriasis or the IGA evaluation (including but not limited to MTX, cyclosporine, acitretin), herbal treatments, or traditional Taiwanese, Korean, or Chinese medicines, and any other biological agent or other systemic medication that could affect psoriasis or the IGA evaluation.

### **6.5.4. Concomitant Therapies for Conditions Other Than Psoriasis**

Every effort should be made to keep participants on stable concomitant medications. If the medication is temporarily discontinued because of abnormal laboratory values, side effects, concurrent illness, or the performance of a procedure, the change and reason for it should be clearly documented in the participant's medical record.

The use of stable doses of nonsteroidal anti-inflammatory drugs is allowed. However, disease modifying agents such as MTX, sulfasalazine, or IM gold are prohibited during the study. Lithium and antimalarial agents may not be used.

The use of corticosteroids for indications other than psoriasis should be limited to situations for which, in the opinion of the treating physician, there are no adequate alternatives. They should be used on a short-term basis, preferably for  $\leq 2$  weeks. Longer term use of corticosteroids should be discussed with the medical monitor or designee and may require discontinuation of study intervention. Inhaled, otic, ocular, nasal or other routes of mucosal delivery of corticosteroids are allowed throughout the study.

### **6.5.5. Concomitant Therapies After Week 52**

After the Week 52 visit, the medication rules outlined above still apply except that most topical therapies are permitted for treatment of psoriasis; ultra-high potency corticosteroids are still prohibited during this period.

The sponsor must be notified in advance (or as soon as possible thereafter) of any instances in which prohibited therapies are administered.

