##### 9.4.1.2. Efficacy Definitions

**Treatment Failure:** Participants who discontinue study treatment due to lack of efficacy or an AE of worsening of psoriasis, or who started a protocol-prohibited medication/therapy during the study that could improve psoriasis are considered treatment failures. The treatment failure rules will be documented in detail in the SAP.

**PASI 50 Responders:** Participants with  $\geq 50\%$  improvement in PASI from baseline.

**PASI 75 Responders:** Participants with  $\geq 75\%$  improvement in PASI from baseline.

PASI 90 Responders: Participants with  $\geq 90\%$  improvement in PASI from baseline.

PASI 100 Responders: Participants with 100% improvement in PASI from baseline.

Loss of PASI 90 Response: Defined as  $< 90\%$  improvement in PASI from baseline after Week 16 in a participant who had achieved  $\geq 90\%$  improvement in PASI from baseline at Week 16.

Loss of 50% of PASI Improvement: Defined as a loss of  $\geq 50\%$  of the improvement in PASI at Week 16 after treatment is withdrawn.

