4.6. Prior and Concomitant Medications

Subjects' prior psoriasis medication history with topical agents, phototherapy, non-biologic systemic therapies, and biologic medications will be summarized by treatment group for the full analysis set for Part 1 and Part 2 of the study. See Section for lists of medications in each category. In addition, reasons for which subjects discontinued previous systemic therapies (contraindication, inadequate response, intolerance [ie, AEs], or other) will be summarized by treatment group.

The number of subjects who received concomitant treatment with a moisturizer for psoriasis will also be summarized through Week 16 for Part 1.

Subjects who received the following concomitant medications will be listed:

- Corticosteroids (intralesional, IV or oral) for indications other than psoriasis and/or psoriatic arthritis
- Intra-articular corticosteroids

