5.1.3.2. Treatment Failure Criteria

Subjects who discontinue study agent due to lack of efficacy, an adverse event (AE) of worsening of psoriasis, or who started a protocol-prohibited medication/therapy during the study that could affect their psoriasis are considered as treatment failures.

The particular protocol-prohibited medications/therapies include:

Topical Therapies:

- Any anti-psoriatic topical therapies used for psoriasis (with the exception of topical moisturizers and shampoos containing tar or salicylic acid only)

Phototherapy or Systemic Therapies:

- Any systemic corticosteroid used for psoriatic arthritis or psoriasis with the exception of intra-articular corticosteroids.
- Any other anti-psoriatic systemic therapy or biologic therapy.
- Phototherapy of UVB or PUVA.
- Any other phototherapy for psoriasis.

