5.1.3.3. Treatment Failure Rules

A subject who meets one or more treatment failure criteria specified in Section 5.1.3.2 will be considered a treatment failure from that point onward. The baseline values will be used for all directly measured endpoints regardless of the actual measurements. Zero will be assigned to improvement and percent improvement, and non-responder status will be assigned to binary response variables.

Treatment failure is assumed to have occurred at the earlier of the following dates:

- Date of discontinuation (DC) of study treatment due to lack of efficacy or
- Date of discontinuation of study agent due to an AE of worsening of psoriasis or
- Start date of a protocol-prohibited medication/therapy during the study that could improve psoriasis

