5.5.2.3. Efficacy Analyses for Long Term Extension

Efficacy in the LTE period (from Week 52 through the end of the study) will be summarized for all subjects who entered LTE.

- The proportion of PASI responses (PASI 50, 75, 90, and 100) will be summarized over time through the end of the study.
- The proportions of subjects achieving an IGA score of cleared (0); an IGA score of cleared (0) or minimal (1); and an IGA score of mild or better (≤ 2) will be summarized over time through the end of the study.
- The percent improvement from baseline in PASI will be summarized over time through the end of the study.
- BSA involved and change from baseline in BSA will be summarized over time through the end of the study.

In addition, PASI responses, IGA responses, percent improvement in PASI, and change in BSA will be summarized at Week 60 and Week 84 after retreatment among guselkumab subjects who were withdrawn from guselkumab at Week 16 and were subsequently retreated upon loss of response or at Week 52 if a loss of response was not observed at or prior to Week 52.

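### Extension response rates are not comparable with rates through Week 52 and cannot be read as response to guselkumab alone: topicals become permitted and the treatment-failure rules stop

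*Protocol*

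**What the plan says.** **Through Week 52.** Protocol 6.5.2 states that topicals that could affect psoriasis "are not permitted at any time during the study", apart from rescue steroids in Part 1. The SAP 5.1.3.2 list of failure-triggering therapies opens with "Any anti-psoriatic topical therapies used for psoriasis", excepting moisturizers and tar or salicylic acid shampoos. Under SAP 5.1.3.3 the consequence runs from the start date onward: "non-responder status will be assigned to binary response variables".

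**After Week 52.** Protocol 6.5.5 keeps the other rules "except that most topical therapies are permitted for treatment of psoriasis; ultra-high potency corticosteroids are still prohibited during this period".

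**LTE analysis.** SAP 5.5.2.3: "Efficacy in the LTE period (from Week 52 through the end of the study) will be summarized for all subjects who entered LTE". It covers PASI and IGA responses, PASI percent improvement and BSA, with further summaries at Weeks 60 and 84 for guselkumab participants withdrawn at Week 16 and later retreated. SAP 5.1.3.6 applies neither treatment-failure rules nor imputation in the LTE, and SAP 5.5.3 repeats that observed data are used.

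**Medication summaries.** The only topical product counted in SAP 4.6 is moisturizer: "The number of subjects who received concomitant treatment with a moisturizer for psoriasis will also be summarized through Week 16 for Part 1". Nothing there covers topical psoriasis therapy in the LTE.

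**The concern.** Two rules change at the same visit: what participants may use, and how its use is counted. A response rate up to Week 52 means response without an added topical. From Week 60, the first LTE assessment in Protocol 1.3.3, the same label means response with or without one. A reader of a table running across Week 52 has no way to see this, and no planned output says how many participants used a topical.

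Retreatment is where it matters most, because efficacy of retreatment is a stated secondary objective (Protocol 3). Retreatment summaries within the main study apply failure rules; those at Weeks 60 and 84 do not. Participants who never lost response are first re-dosed at Week 52 (Protocol 6.1), so all their retreatment follow-up falls in the period when topicals are allowed.

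**Working it through.** The plan states no LTE rate, so there is no figure to reproduce. The check sets the rules side by side.

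| | Through Week 52 | LTE |
|---|---|---|
| Anti-psoriatic topicals | Barred, except Part 1 rescue (Protocol 6.5.1, 6.5.2) | Most allowed (Protocol 6.5.5) |
| Threshold met after starting a topical | Non-responder (SAP 5.1.3.2, 5.1.3.3) | Responder (SAP 5.1.3.6, 5.5.3) |
| Threshold met after starting a prohibited systemic | Non-responder (same sections) | Responder (same sections) |
| Missing binary data | Non-responder, except no imputation after retreatment or initiation (SAP 5.1.3.6) | Observed only |
| Topical use visible in outputs | Failure and rescue listings (SAP 4.2); moisturizer count to Week 16 (SAP 4.6) | No summary of permitted topicals |

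**Example.** A Part 2 participant starts a topical steroid between Weeks 36 and 44 and has IGA 1 at every later visit. The plan counts a non-responder at Weeks 44 and 52 and, if the participant enters the LTE, a responder at Week 60, with no change in skin or treatment.

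**Would restoring the failure rule be enough?** Not clearly. Protocol 9.4.1.2 says that those who "started a protocol-prohibited medication/therapy during the study that could improve psoriasis are considered treatment failures", and most LTE topicals are no longer prohibited. The SAP 5.1.3.2 list names any anti-psoriatic topical, but as an example of prohibited therapy. The two could be read differently, so a rule naming topical use is needed.

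**Illustration only.** Every input below is assumed.

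1. *Observed rate against a rate counting topical users as non-responders.* With observed rate R and share t of responders who used a topical, the second rate is R × (1 − t) and the gap is R × t.

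| R | t = 5% | t = 10% | t = 20% | t = 30% |
|---|---|---|---|---|
| 70% | 66.5% | 63.0% | 56.0% | 49.0% |
| 85% | 80.75% | 76.5% | 68.0% | 59.5% |

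The gap runs from 0.70 × 0.05 = 3.5 points to 0.85 × 0.30 = 25.5 points, whatever the number of participants.

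2. *Responders who would not have responded on guselkumab alone.* With response g on guselkumab alone, share a of the rest adding a topical, and success s with it, the excess is (1 − g) × a × s. Low case: 0.2 × 0.3 × 0.2 = 1.2 points. High case: 0.4 × 0.6 × 0.4 = 9.6 points.

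These are different quantities. The first also removes topical users who would have responded anyway. If a topical never turns a responder into a non-responder, the guselkumab-alone rate among those observed lies between the two reported rates.

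**The case against.** The strongest reply is that observed data in the LTE is a deliberate, prespecified choice describing participants as treated under the LTE rules. The LTE is open-label and uncontrolled, carries no hypothesis, and admits only participants whom the investigator judges to have benefited (Protocol 6.1). Part 2 gives continuous treatment through Week 52 with topicals barred and failure rules applied, and Protocol 4.2 names it as the maintenance evidence. Retreatment response is already summarized within the main study at, for example, 4, 8 and 12 weeks. All of this stands. It limits the point to reporting and is why the observed summary should stay.

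It also rules out some stronger readings that a reader might infer:

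- *That adding a topical makes a participant a responder.* It does not; the PASI or IGA threshold must be met at that visit.
- *That the LTE is the only evidence on maintenance or retreatment.* It is the only efficacy evidence beyond Week 52, which is narrower.
- *That a step at Week 60 would show a topical effect.* Missing-data handling also changes, and withdrawn participants never retreated before Week 52 are dosed then.

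SAP 5.1.3.5 applies failure rules to topical steroid use after Week 20 and gives no end date, which might seem to reach the LTE. It belongs to the Part 1 rescue rules, and SAP 5.1.3.6 and 5.5.3 address the LTE directly, so they govern.

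For prohibited therapy the gap is smaller. Protocol 6.5 calls for stopping study treatment unless the medical monitor agrees otherwise, and SAP 4.5 summarizes major deviations, including disallowed treatments, through the end of the LTE. Neither covers permitted topicals.

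**Conclusion.** The point holds as a reporting gap. LTE response rates, including those at Weeks 60 and 84 after retreatment, follow different medication and counting rules from rates through Week 52. They cannot be compared directly with those rates or read as response to guselkumab alone. PASI percent improvement and BSA share the limitation.

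The size is unknown. The ranges of 1.2 to 9.6 points and 3.5 to 25.5 points rest wholly on assumed inputs, and a reader should not infer that LTE rates are inflated by any particular amount. Nor do the documents support inferring that the confirmatory results are affected: the co-primary and major secondary tests are at Week 16, and the main-study summaries keep their failure rules.

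**What to change.** 1. **SAP 4.6:** tabulate topical psoriasis therapy, and any prohibited psoriasis therapy, used in the LTE by class, potency (for topical steroids) and start week.
2. **SAP 5.5.2.3:** keep the observed-data summary. Beside each PASI and IGA response rate, including Weeks 60 and 84, add a rate counting participants as non-responders from first such use in the LTE, with moisturizers and permitted shampoos excepted. Use the same denominator, so that the two rows differ only in this rule. Label it a conservative lower bound, because it also reclassifies participants who would have responded without the topical.
3. **LTE tables and plots:** footnote that the concomitant-therapy and data-handling rules both change at Week 52.

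The cost is SAP wording, one table and one extra row per LTE response table. Protocol 6.5 already requires therapies to be recorded until 12 weeks after the last dose, and Protocol 1.3.3 schedules concomitant therapy review at every LTE visit. No new data or visits are needed, and the therapies permitted do not change. The drawback is that, over a long extension, brief use of a permitted product makes a participant a non-responder for all later visits in the supplementary row. That row should therefore never be shown without the observed rate.
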